#### **6.4.4 Analysis of Secondary Outcomes of Interest**

1. IMPACT independent predictors: This secondary objective will identify independent variables that are associated with IMPACT scores. Multivariable logistic and linear regression models will be developed for categorical and continuous independent variables, respectively, and tested for association with each IMPACT score. Those independently associated with the IMPACT will be reported and factored into the multivariable regression for the primary endpoint.
2. Internal consistency and reliability will be measured by Cronbach alpha testing, item-response theory (IRT), and correlation between initial and followup surveys for patients completing both within one month.
3. The MCID for each module and subscale will be calculated using an anchor-based approach with a single item that addresses each patient's overall satisfaction.

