## ABSTRACT

**Context:** Maxillofacial trauma literature is dominated by objective, physician-rated outcomes, leaving a gap in our understanding of the patient experience.

**Objectives:** The primary objective of this study is to validate a novel patient-reported outcome Measure (PROM) for maxillofacial trauma: Integrated Modular Patient-Reported Outcome Assessment for Craniomaxillofacial Trauma (IMPACT).

**Study Design:** Prospective, multi-institutional survey study.

**Setting/Participants:** Patients presenting for routine clinic follow-up for maxillofacial trauma at high-volume trauma centers throughout the United States will be screened. Adults with fractures of the upper face, midface, mandible, and/or facial soft tissue injury within the last 12 months will be included.

**Study Procedures, Interventions and Measures:** Participants providing informed consent will complete the appropriate IMPACT survey modules based on their fracture pattern: IMPACT-N for involvement of the nasal region, IMPACT-O for the orbital region, and/or the IMPACT-J for the jaw. Patients will also complete the 15 Dimension (15D) QOL survey as a control. Surveys will be collected at two consecutive appointments. Independent variables related to the trauma will be abstracted for analysis.

**Main study outcome measures:** The primary objective will be to determine criterion validity of each IMPACT module and subscale via correlation with the 15D (Pearson's r). Secondarily, we will analyze internal validity and reliability (via Cronbach alpha and Item Response Theory [IRT] analysis). Consecutive surveys will be compared for reliability. The minimally clinically important difference (MCID) will be calculated using an anchor-based approach. Finally, IMPACT scores will be analyzed across independent variables including sociodemographic variables, trauma details, and management approach.

---

---

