### **2.2 Secondary Objectives**

1. Analyze IMPACT module and subscale scores across baseline sociodemographic, injury, and treatment variables in order to understand which factors influence QOL.
2. Analyze the reliability of each IMPACT module and subscales.
3. Determine the sensitivity to change for IMPACT modules and subscales.
4. Calculate the minimally clinically important difference (MCID) for each IMPACT module and subscales.

---

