### 6.2 Secondary Endpoints

1. Identification of independent predictors of IMPACT scores including baseline sociodemographic, injury, and treatment variables.
2. Determine the reliability of IMPACT scores.
3. Calculate the change in IMPACT scores at subsequent clinic visit(s).
4. Calculate the MCID for each IMPACT module and subscale.

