### 6.4 Statistical Methods

All analysis will be performed by the host institution. Effect sizes with 95% confidence intervals (CI) will be provided for every applicable measurement. The analytical plan will be reviewed by professional biostatisticians at the host institution.

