#### 6.4.1 Baseline Data

The following chart review variables will be abstracted after informed consent is obtained and the initial survey is completed. This data will be summarized descriptively with average, median, range, interquartile range, and standard deviation, as appropriate. Each variable will then be tested for association with IMPACT scores on univariable analysis. Clinically or statistically significant variables will then be included in subsequent multivariable testing.

---

---

- Sociodemographic data: Age, sex, race, ethnicity, marital status, smoking status, payor type (private, medicare, Medicaid, government, none / self-pay, or other), and Social vulnerability index (SVI) values based on home address.
  - SVI: A measure of social vulnerability assigned to each zip code or census tract by the Center for Disease Control and Prevention.
- Trauma data: Mechanism, concomitant multisystem trauma, airway status, level of care (discharged from emergencet room, floor/stepdown admit, intensive care admit), presenting signs or symptoms (cranial nerve weakness, trismus, malocclusion, visual impairment), description of facial trauma, comprehensive facial injury (CFI) score, and Facial Injury Severity Score (FISS).
  - CFI: An objective scale based on maxillofacial imaging and clinical exam providing an integer that represents fracture severity by correlating it with the operative time for repairing each fracture.
  - FISS: An objective scale based on maxillofacial imaging and clinical exam providing an interger that represents the objective severity of facial trauma by correlation with the cost of management.
- Management data: Treatment (observation, bedside intervention, or surgical repair), type of surgical repair (closed reduction, open reduction, internal fixation, external fixation, and maxillomandibular fixation [MMF]), hospital length of stay (days), disposition (home versus medical facility)
- Objective complications: Wound infection or dehiscence, Malunion or nonunion, hardware extrusion, or any unplanned return to the emergency department, admission or reoperation related to the facial injury.
- Survey metadata: time from trauma to survey (days), time from intervention to survey (if applicable; days), presence of maxillomandibular fixation at the time of the survey.

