#### 6.4.2 PROM Scoring

- IMPACT Scoring: IMPACT modules consist of 8-16 Likert scale questions from 0-4 (5-point). The total module score will be standardized by taking the average of all questions in a module then multiplying x25, giving a total module score of 0-100 with higher scores indicating more worse QOL impairment. The pain scale will be reported separately and the final score will be the patients pain score from 0-10 multiplied by 10 for a final pain score of 0-100. For the initial analysis, partially completed surveys with any number of missing answers will be included. Individual subscales for each module will also be given a “subtotal” score which is the average of the Likert scale answers in that subscale, multiplied by 25 for a standardized score from 0-100.
- 15D Scoring: The 15D is scored using a non-linear, copyright algorithm that accounts for baseline demograpic variability. It is available here: <https://15d-instrument.net/15d/> (15D©/Harri Sintonen). The code for this analysis already been released to the host institution for use in the analysis of this study.

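### Section 6.4.4 item 1 chooses logistic or linear regression by the type of the predictor, although the outcome is always an IMPACT score on 0-100

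*Protocol*

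**What the plan says.** Section 6.4.4 item 1 of the protocol gives the model for the predictor analysis: "Multivariable logistic and linear regression models will be developed for categorical and continuous independent variables, respectively, and tested for association with each IMPACT score". The word 'respectively' pairs logistic regression with categorical independent variables and linear regression with continuous ones.

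Elsewhere the protocol treats the IMPACT score as the outcome and the patient, injury and treatment variables as predictors:

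- Abstract: "IMPACT scores will be analyzed across independent variables including sociodemographic variables, trauma details, and management approach".
- Section 2.2, objective 1: the scores are analysed across these variables "in order to understand which factors influence QOL".
- Section 6.2, endpoint 1: "Identification of independent predictors of IMPACT scores including baseline sociodemographic, injury, and treatment variables".

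Section 6.4.2 scores each module by averaging its items and multiplying by 25, "giving a total module score of 0-100". Subscales are scored the same way, and pain is rescaled to the same range. Section 6.4.1 lists the predictors. Many are categorical, some with more than two levels, for example "Treatment (observation, bedside intervention, or surgical repair") and a payor variable with six categories. Section 6.4 promises: "Effect sizes with 95% confidence intervals (CI) will be provided for every applicable measurement".

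**The concern.** The family of a regression model is set by the scale of its dependent variable. Categorical and continuous predictors can sit together in one linear model, the former as indicator variables. The sentence in 6.4.4 ties the choice to the predictors instead.

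The only way to carry it out as written is to turn the model round, so that the characteristic is the response and the IMPACT score is a covariate. For every categorical predictor the output is then the odds of, say, having had surgical repair per IMPACT point. That does not say how far IMPACT scores differ between treatment groups after adjustment. The effect sizes and confidence intervals for much of the predictor list would be on a scale that does not suit the stated aim of finding predictors of IMPACT scores.

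**Working it through.** **Step 1. Scale of the outcome.** From 6.4.2: items run 0-4, so a module or subscale score runs from 0 × 25 = 0 to 4 × 25 = 100. Pain runs from 0 × 10 = 0 to 10 × 10 = 100. All IMPACT outcomes are numeric on 0-100, and no section gives a cut-off that would make one binary.

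**Step 2. Possible readings of the sentence.**

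- *IMPACT is the outcome, logistic for categorical predictors.* This cannot be done: a binary logistic model does not accept a 0-100 response.
- *The characteristic is the response, IMPACT a covariate.* This can be fitted for a two-level characteristic. It reverses the roles given in 2.2 and 6.2, and a plain binary logistic model does not fit treatment (three levels) or payor (six levels).
- *'Independent' is a slip for 'dependent'.* Linear regression then serves the 0-100 scores, and logistic regression has no categorical IMPACT outcome in this protocol to serve.

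All three lead to the same correction.

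**Step 3. What the reversed model reports.** Take a binary characteristic and an IMPACT score that, given the other covariates, is roughly normal with the same residual SD in both groups and a mean difference of D points. The odds ratio per IMPACT point is then

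OR = exp(D / SD²).

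The protocol gives neither D nor SD. Both are assumed here: D = 10 points, and SD = 15, 20 or 25.

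| Residual SD | D / SD² | OR per point | Points implied by an OR of 1.025, ln(1.025) × SD² |
|---|---|---|---|
| 15 | 10/225 = 0.0444 | 1.045 | 5.6 |
| 20 | 10/400 = 0.0250 | 1.025 | 9.9 |
| 25 | 10/625 = 0.0160 | 1.016 | 15.4 |

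One difference in points gives three odds ratios. Conversely, one odds ratio stands for anything from 5.6 to 15.4 points, depending on the spread of the score.

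**Step 4. Check by simulation.** Module sizes follow from 6.5 and 3.2.2: 500 × 30% = 150 (orbital), 500 × 40% = 200 (nasal), 500 × 60% = 300 (jaw), and 500 (general). Each setting had 2,000 simulated trials. Further assumptions: a binary characteristic with log-odds slope 1.2 per SD of injury severity; IMPACT rising 5 points per SD of severity; severity in both models.

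- Median odds ratio per point: 1.046-1.047 at SD 15, 1.026 at SD 20 and 1.016 at SD 25, across all four sizes.
- Mean difference from the linear model: 9.89 to 10.07 points in all 12 settings, against a true 10.
- Same decision at p < 0.05 in both models: 96.9% to 100% of trials.
- False positives with no true effect (SD 20): 4.7% and 4.4% for linear, 4.4% and 4.2% for logistic, at n = 150 and 500.

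The reversed model therefore detects about the same associations but reports them on an unsuitable scale.

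**The case against.** The strongest reply is that the stated endpoint is the identification of predictors, and identification survives. Both models reach the same decision in 97-100% of trials, so the set of variables carried into the adjusted primary model hardly changes. This stands, and it limits the point to the reported estimates. It was shown for a binary characteristic with the same covariates in both models; three- and six-level variables were not simulated.

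A second reply is that the sentence is a slip that the biostatistical review promised in 6.4 would catch. That is plausible and makes it less likely that reversed models will be run. It does not correct the sentence, which is wrong on each reading. An unseen SAP could define a binary IMPACT outcome, but this protocol does not.

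Three stronger inferences are tempting and should not be drawn:

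- *That logistic results would rank a smaller QOL effect above a larger one across modules.* An example can be built with 6 points at SD 15 against 10 points at SD 25. But 6/15 = 10/25 = 0.40 SD, so the reversal comes from expressing the odds ratio per point; per residual SD the two effects tie. The protocol plans no ranking across modules and does not claim that a point means the same on each.
- *That the results could not be compared with the MCID.* An odds ratio is indeed not in points, but no section plans to set predictor effects against the MCID.
- *That power would be lost.* In an illustration with n = 150, SD 20 and a 9-point difference, splitting the score at its median cut power from about 78% to about 60%. The protocol plans no such split, and the reversed logistic model kept about 78%.

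**Conclusion.** The point holds as an error of model specification in the protocol text. Section 6.4.4 item 1 selects the regression by predictor type, while 6.4.2 puts every outcome on 0-100 and 2.2 and 6.2 make IMPACT the outcome. Taken literally, the effects reported for categorical predictors would be odds ratios per IMPACT point: about 1.05, 1.03 or 1.02 for the same 10-point difference, under assumed residual SDs of 15, 20 and 25. These are not the adjusted differences that suit the aim and the promised effect sizes.

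Its reach is small. It concerns the estimates of one secondary analysis. Predictor selection hardly changes under the simulated conditions, and the Pearson criterion of r > 0.4 with p < 0.05 in 6.4.3 does not depend on it. A reader might infer that the primary validity result is at risk; the documents do not support that. That the rule is wrong follows from the text alone; only the size of the illustration rests on assumed values.

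**What to change.** Replace the sentence in 6.4.4 item 1 with:

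*For each IMPACT module and subscale score (dependent variable, continuous 0-100), one multivariable linear regression will be fitted with the selected predictors together, continuous predictors entered as such and categorical predictors as indicator variables; adjusted mean differences or slopes will be reported with 95% CI.*

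Drop logistic regression unless a binary IMPACT outcome with a prespecified cut-off is defined.

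The cost is one sentence changed before analysis. No new data or patients are needed, and the primary criterion stays as it is. The correction need go no further: which survey supplies the score, and how variables that exist only for treated patients are handled, are separate matters that do not follow from this error.

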## **3 INVESTIGATIONAL PLAN**

This study will be a multi-institutional field test for the IMPACT. The survey will be administered to maxillofacial trauma patients presenting for routine clinic follow-up along with a control QOL survey. IMPACT module and subscale scores will undergo psychometric testing to determine validity and reliability.

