## 5 STUDY EVALUATIONS AND MEASUREMENTS

### 5.1 Screening and Monitoring Evaluations and Measurements

#### 5.1.1 IMPACT Survey

The IMPACT is a PROM with 4 independent modules. The first is a “General Module” for all patients with maxillofacial trauma. The remaining three modules were designed for specific fractures involving nasal, orbital, and/or jaw regions (Table 1). Each module takes 2-5 minutes to complete for a total of 2-20 minutes/survey depending on fracture pattern.

1. General Module (IMPACT-G)
  - a. **Target patients:** All maxillofacial trauma patients
  - b. **Number of questions:** 21
  - c. **Structure:** 5-point Likert Scales (except for a single “pain score” from 0-10)
  - d. **Subscales (4):** Overall Facial Appearance, Psychosocial Function, General Symptoms, Pain
2. Nasal Module (IMPACT-N)
  - a. **Target patients:** Fractures of the nasal bones and/or sinuses
  - b. **Number of questions:** 15
  - c. **Structure:** 5-point Likert Scales
  - d. **Subscales (2):** Nasal Function, Nasal Appearance
3. Orbital Module (IMPACT-O)
  - a. **Target patients:** Fractures of the orbital walls or rim
  - b. **Number of questions:** 15
  - c. **Structure:** 5-point Likert Scales
  - d. **Subscales (2):** Orbital Function, Orbital Appearance
4. Jaw Module (IMPACT-J)
  - a. **Target patients:** Fractures of the mandible or upper jaw
  - b. **Number of questions:** 20
  - c. **Structure:** 5-point Likert Scales
  - d. **Subscales (2):** Jaw Function, Jaw Appearance

**Table 1:** User guide for the Integrated Modular Patient-Reported Outcome Assessment for Craniomaxillofacial Trauma (IMPACT).

IMPACT Modules	IMPACT-G	IMPACT-N	IMPACT-O	IMPACT-J
Facial Soft Tissue Injury	X			
Upper Facial Third Fractures				
Frontal Sinus	X	X		
Superior orbital rim	X		X	
Middle Facial Third Fractures				
Nasal bones and/or septum	X			
Facial sinus fractures	X	X		
Naso-orbito-ethmoid	X	X	X	
Orbital rim and/or wall	X		X	
Zygomaticomaxillary complex (ZMC)	X		X	X
Zygomatic arch fracture	X			X
Upper dentoalveolar or palate	X			X
Le Fort I	X	X		X
Le Fort II/III	X	X	X	X
Lower Facial Third Fractures				
Mandible	X			X
Lower dentoalveolar	X			X

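### Alpha and IRT are planned for modules and subscales, but no stated analysis tests whether the items form those subscales or justify a single module total

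*Protocol*

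**What the plan says.** Section 6.4.4, item 2, names the methods: "Internal consistency and reliability will be measured by Cronbach alpha testing, item-response theory (IRT), and correlation between initial and followup surveys", the last for patients who complete both surveys within one month. That sentence does not name a level of analysis, but two other places do. Section 2.2 lists as an objective "Analyze the reliability of each IMPACT module and subscales", and section 3 says that "IMPACT module and subscale scores will undergo psychometric testing to determine validity and reliability". The abstract words the same analyses differently: "we will analyze internal validity and reliability (via Cronbach alpha and Item Response Theory [IRT] analysis".

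Section 5.1.1 builds each module from named subscales:
- IMPACT-G: "Overall Facial Appearance, Psychosocial Function, General Symptoms, Pain"
- IMPACT-N: "Nasal Function, Nasal Appearance"
- IMPACT-J: "Jaw Function, Jaw Appearance"
- IMPACT-O: the same function and appearance pair as N and J

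Section 6.4.2 then pools the items: "The total module score will be standardized by taking the average of all questions in a module then multiplying x25". Each subscale gets its own 0-100 subtotal, and the 0-10 pain item is reported separately. Under section 6.4.3 a module or subscale counts as valid if its correlation with the 15D has p < 0.05 and r > 0.4. The protocol names no factor analysis, dimensionality check or other structural criterion.

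**The concern.** The primary objective is the validity of each module and subscale. Part of that question is whether the items assigned to a subscale belong together, and whether function and appearance items can be averaged into one meaningful number. Alpha depends on the number of items and their average intercorrelation. It does not test whether the items share one construct. Calling it internal validity, as the abstract does, credits it with something it cannot show.

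The other planned statistics do not fill the gap. Subscale alphas describe consistency within each set of items and say nothing about how the sets relate. Initial-to-follow-up correlation can be high for a composite of unrelated parts. So can correlation with the 15D, as shown in the working. A module total could therefore be published as a validated single scale with no evidence that it is one.

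**Working it through.** **The plan's own figures.** The protocol gives no alpha or other reliability figure to reproduce. The relevant planned number is 150 completers per module (section 6.5). Its enrolment figure reproduces: 150 / 0.30 = 500.

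**Inputs from the protocol.** Section 5.1.1 gives 15 items for N, 15 for O, 20 for J and 21 for G. One G item is the separately reported 0-10 pain score, which leaves 20 Likert items. The subscales are those listed in section 5.1.1.

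**Assumptions.** The protocol gives neither items per subscale nor inter-item correlations. I assume near-even splits, an equal correlation r_w within each subscale (0.3, 0.4 or 0.5), and a correlation r_b = 0 between items of different subscales. I also assume that the pain item is the whole Pain subscale, so the Likert items of G form three subscales.

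**Formula.** For k items in subscales of size m, let S = sum of m(m-1). Then

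V = k + r_w S + r_b [k(k-1) - S], and standardised alpha = k/(k-1) x (1 - k/V).

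Worked case for IMPACT-J, 10+10, r_w = 0.5, r_b = 0: S = 90 + 90 = 180; V = 20 + 90 = 110; alpha = (20/19)(1 - 20/110) = 0.86.

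| Module (assumed split) | S | r_w = 0.3 | r_w = 0.4 | r_w = 0.5 |
|---|---|---|---|---|
| J, 20 items (10+10) | 180 | 0.77 | 0.82 | 0.86 |
| N or O, 15 items (8+7) | 98 | 0.71 | 0.77 | 0.82 |
| G, 20 Likert items (7+7+6) | 114 | 0.66 | 0.73 | 0.78 |

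**Sensitivity.**
- Uneven split: J as 15+5 gives 0.82 at r_w = 0.3 and 0.90 at 0.5.
- Related subscales: with r_b = 0.2, J (10+10) at r_w = 0.5 gives V = 20 + 90 + 0.2 x 200 = 150 and alpha = (20/19)(1 - 20/150) = 0.91. Moving from unrelated to related subscales shifts alpha only from 0.86 to 0.91.
- Module length: section 6.4.2 gives 8-16 Likert questions per module, which conflicts with section 5.1.1. With 8 items (4+4) and r_b = 0, alpha is 0.54 at r_w = 0.3 and 0.69 at 0.5. With 16 items (8+8) it is 0.83 at 0.5.

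**Subscale alphas.** With 8+7 items and r_w = 0.5 these are 8 x 0.5 / (1 + 7 x 0.5) = 0.89 and 7 x 0.5 / (1 + 6 x 0.5) = 0.88, whatever the correlation between the subscales.

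**The 15D criterion.** Two uncorrelated subscales can each correlate 0.4 with the 15D, since 0.4² + 0.4² = 0.32, well below 1. If they have equal variance, as in the 10+10 case, their total correlates (0.4 + 0.4)/√2 = 0.57 with it. The total can thus exceed the 0.4 mark even though its two parts are unrelated.

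**The case against.** The strongest objection is that this is detail for a statistical analysis plan. The IRT model, dimensionality checks and choice of reliability coefficient often sit there; none is at hand, and section 6.4 promises biostatistical review. That stands for the IRT model. It does not dispose of the point. The protocol itself fixes the pooled total, reliability at module level, the internal validity label and a validity rule with no structural element, and it does so for its primary objective.

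Several stronger readings are tempting, and the documents do not support them:
- A reader might infer that reliability is assessed only for whole modules. Sections 2.2 and 3 cover subscales too.
- A reader might infer that the IRT estimates will be wrong. The protocol does not say that a one-dimensional model will be fitted to a module, and multidimensional IRT is also IRT.
- A reader might infer that pairing function with appearance breaks unidimensionality by construction. The two may well correlate in one injured region, and a general factor may exist. The plan simply does not look.
- A reader might infer that any module would pass a conventional alpha cut-off. The protocol sets no cut-off, and the shorter modules and G can give values below 0.7.

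It is also fair that zero correlation between subscales is an extreme case, and that reliability is a secondary objective. The calculation shows that alpha cannot detect the problem; it does not predict what the data will show.

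**Conclusion.** The point holds in this form: reliability is planned at both levels, but nothing stated tests the subscale structure or the case for a single module total before each is scored 0-100 and judged on the 15D correlation. Alpha cannot stand in for that test. Under the assumed even splits and zero between-subscale correlation it reaches 0.71 to 0.86 for N, O and J at the lengths in section 5.1.1, and 0.66 to 0.78 for G. These values rest on assumed splits and correlations and on item counts that sections 5.1.1 and 6.4.2 state differently. No sample size or primary correlation changes. What changes is whether a module total may be described as one scale.

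**What to change.** In section 6.4.4, item 2:
1. Before alpha and IRT, fit a confirmatory factor model for ordinal items with the subscale structure of section 5.1.1, keeping the 0-10 pain item separate.
2. Report alpha or omega for each multi-item subscale.
3. Fit a one-dimensional IRT model only where the factor model supports one dimension.
4. For module totals, report stratified alpha or omega-hierarchical, and present a total as a single scale only if a general factor is supported. Stratified alpha gives the reliability of a composite and is not itself evidence of one construct. For the two-subscale modules, the correlation between the two factors, with its confidence interval, is the main evidence.
5. Drop internal validity as a label for alpha in the abstract.
6. Reconcile the item counts in sections 5.1.1 and 6.4.2, and state the items per subscale.

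The cost is some extra analysis on data already planned, with no new patients or visits. Precision is the real limit: 150 completers give 150/15 = 10 per item for N and O and 150/20 = 7.5 for J. An ordinal two-factor model for J has 20 x 4 = 80 thresholds, 20 loadings and one factor correlation, 101 parameters in all, and partly completed surveys are retained. Fit results should be read with that in mind. The sponsor must also accept that a module total may not be supported, in which case subscale scores would be reported instead.

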### **3.2 Study Duration, Enrollment and Number of Sites**

#### **3.2.1 Duration of Study Participation**

The study duration per subject will be up to 3 months, with 1 day of screening and initial survey completion, then 1 additional follow-up survey at a subsequent appointment. Each survey takes 2-20 minutes to complete depending on complexity of the fracture pattern, for a possible total study commitment of 4-40 minutes for each participant.

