#### **4.1.2 Procedures: Follow-up Visit**

IMPACT and 15D Survey Completion: A member of the research team will assign and administer the appropriate IMPACT modules for each patient based their fracture pattern (preferably on a tablet, but may complete on paper if needed). Alternatively, patients will be

---

offered the opportunity to provide their email address to complete the follow-up survey at home at a later date.

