### **7.5.3 Potential Benefits of Study Participation**

Potential benefits are an additional opportunity for the patients to share symptoms and experiences while recovering from facial trauma, which may help the treating physician better understand how to care for each patient. This will also help contribute to an improved understanding of the recovery process after suffering facial trauma.

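### Retest reliability is estimated from all survey pairs completed within one month, with no condition that the recovering patient be unchanged

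*Protocol*

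**What the plan says.** - **Retest analysis.** Section 6.4.4 item 2 lists Cronbach alpha, item response theory and the "correlation between initial and followup surveys for patients completing both within one month". It gives no other rule for choosing the pairs.
- **One pair per patient.** Section 3.2.1 provides an initial survey and one further survey: "The study duration per subject will be up to 3 months". Section 4.1 places the two surveys at consecutive routine appointments at any time in the year after injury.
- **Change as an outcome.** Section 2.2 item 3 is to "Determine the sensitivity to change for IMPACT modules and subscales". The matching endpoint, section 6.2 item 3, is the change in score at the later visit, with no minimum interval.
- **State of the patients.** Section 7.5.3 speaks of patients who "share symptoms and experiences while recovering from facial trauma".
- **Clinical state at survey.** Section 6.4.1 lists "time from intervention to survey (if applicable; days), presence of maxillomandibular fixation at the time of the survey" and also lists complications. None of these is used to select retest pairs. The variables are "abstracted after informed consent is obtained and the initial survey is completed". Under section 4.1.2 patients may instead be "offered the opportunity to provide their email address to complete the follow-up survey at home at a later date".

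**The concern.** A test-retest coefficient estimates measurement error only if what is measured has stayed the same between the two occasions. Here the pairs come from trauma follow-up, where true change is expected and is itself an object of study. A within-patient difference then contains both error and recovery. If recovery is uneven, the ranking of patients shifts between visits and the correlation falls, however precise the instrument is.

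Reliability is a secondary objective for an instrument that section 1.1 intends for future studies. Under the rule as written, a low retest coefficient could mean a noisy questionnaire or patients healing at different speeds, and the analysis could not tell which.

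**Working it through.** **Which pairs enter which analysis.** Each patient supplies one pair. Pairs of one month or less form the retest set. The change endpoint has no lower time limit, so as written it takes these pairs and the longer ones. The two sets overlap but are not identical.

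**The plan's own figures.** The protocol states no retest coefficient, precision or expected number of one-month pairs. Its recruitment figure reproduces: 150 / 0.30 = 500 (section 6.5). That implies 150 orbital-module patients, used below.

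**Size of the understatement (illustration; all inputs assumed).** Let the true-score SD be 20 (variance 400), the error variance Ve, and the individual true change independent of baseline with SD s. Then

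r = 400 / sqrt[(400 + Ve)(400 + Ve + s²)]

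Reliability 0.90 gives Ve = 400/0.90 − 400 = 44.4. Reliability 0.80 gives Ve = 100.

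| SD of true change | r if true 0.90 | r if true 0.80 |
|---|---|---|
| 0 | 0.90 | 0.80 |
| 5 | 0.88 | 0.78 |
| 10 | 0.81 | 0.73 |
| 15 | 0.73 | 0.66 |
| 20 | 0.65 | 0.60 |

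A uniform shift has s = 0 and leaves r at its true value. If those with worse scores improve more (change negatively related to baseline), r falls further. With true 0.90 and change SD half the observed baseline SD, r is 0.80 at correlation 0 and 0.75 at −0.5.

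**Only some pairs change.** Let a share p change with mean 15 and SD 15, so s² = 225p + 225p(1 − p). With true reliability 0.90, r is 0.86, 0.81 and 0.77 for p = 10%, 25% and 50%.

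**Absolute agreement.** With mean shift m = 15p, ICC = 800 / [444.4 + (444.4 + s²) + m²]. At p = 50%, s² = 168.75 and m² = 56.25, so ICC = 0.72 against r = 0.77. If every pair changes, s² = 225 and m² = 225, so ICC = 0.60 against r = 0.73. The ICC counts mean recovery as error and r does not.

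**What a screen recovers.** Start from p = 50% and remove a fraction of the changers. For 70% removed, the share kept is 0.50 + 0.15 = 0.65 and changers are 0.15/0.65 = 0.231 of it. Then s² = 91.9, m² = 12.0, r = 0.82 and ICC = 0.81.

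| Changers removed | Pairs kept | r | ICC |
|---|---|---|---|
| none | 100% | 0.77 | 0.72 |
| 50% | 75% | 0.80 | 0.77 |
| 70% | 65% | 0.82 | 0.81 |
| 90% | 55% | 0.86 | 0.86 |

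If every pair changes and exclusion is unrelated to the size of the change, the ICC stays at 0.60.

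**Precision after the screen.** If all 150 orbital patients return within one month and 65% are kept, 97.5, or about 98, pairs remain. For two ratings, F = (1 + 0.81)/(1 − 0.81) = 9.53. Dividing and multiplying by the 97.5% point of F on 97 and 97 degrees of freedom (about 1.49), then converting back by (F − 1)/(F + 1), gives about 0.73 to 0.87.

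**The case against.** Choosing a stable subset and the form of the ICC is often left to a SAP, and one not shown here may do so. This does not remove the point: the protocol states its retest rule, that rule is based on time alone, and following it produces the mixture described.

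The one-month limit is a real safeguard when participation can last three months. Enrolment up to 12 months after injury means that some pairs may come from stable patients. Both stand, and both limit the size of the problem.

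A reader might infer that the protocol contradicts itself by calling the same difference error in one place and signal in another. It does not go that far. Section 6.4.4 gives no analysis set for sensitivity to change, the sets only overlap, and using two surveys for both purposes is not an error in itself.

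A reader might also infer that the clinical variables stop at the first survey. Section 6.4.1 says when abstraction takes place and sets no cutoff. Section 7.3.1 draws the data from the medical record, so a survey done at home does not prevent charted events from being captured. All that is needed is confirmation that MMF status and event dates run to the second survey.

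The strongest objection concerns the remedy. Replacing r with an agreement ICC could make matters look worse: with half the changers removed, the screened ICC of 0.77 only equals the unscreened r. The screen also targets events and not ordinary healing, and the removal rates above have no basis in the protocol. This stands, and it is why both coefficients should be reported and the screen not presented as a cure.

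**Conclusion.** The point holds in limited form. Selecting retest pairs by time alone lets uneven recovery lower the coefficient. The direction is conservative, provided that true change is unrelated or negatively related to the baseline score. The size cannot be computed from the protocol: 0.88 to 0.65 for a true 0.90 rests on an assumed true SD of 20 and change SDs of 5 to 20, and nothing in the protocol places the study within that range.

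It would be wrong to conclude that IMPACT will be found unreliable or that its validation is compromised. No reliability threshold is set. Cronbach alpha, the IRT analysis and the primary correlation with the 15D are unaffected. Only the retest part of secondary objective 2 is touched. The change is worth making because it is cheap and because a low coefficient would otherwise be uninterpretable.

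**What to change.** In section 6.4.4 item 2 or in the SAP:

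1. Make the main retest analysis the one-month pairs with no intervention and no recorded complication between the surveys, and with the same MMF status at both.
2. Confirm that MMF status and the dates of interventions and complications are recorded up to the second survey, including when it is completed at home.
3. In that subset, report an absolute-agreement ICC with 95% CI alongside Pearson's r. The ICC also counts a mean shift as error, so a gap between the two shows systematic change.
4. Keep the all-pairs one-month correlation as a secondary result, since the subset may differ from the full sample.
5. State that sensitivity to change uses all pairs.

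**Cost.** Wording, plus a check on variables already listed; no new survey item and no change in sample size. There will be fewer pairs and wider intervals, as shown above for the orbital module, and wider still if many patients return after one month. Ordinary healing passes the screen, so part of the bias remains and the report should say so.
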